4.5 Subgroup analysis

Exploratory analysis may be carried out to assess the relationship of cellular activation with the targeted subgroups:

- Patients on ECMO within 7 days vs 7+ days
- Patients with and without AKI

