2.2 Secondary outcomes

Clinical outcomes

1. Serum haemoglobin levels.
2. Time to wean from ECMO.
3. Percentage of patients weaned from ECMO within 7 days
4. AKI as defined by the KDIGO pediatric definition (Table 1)
5. AKI as defined based on the neonatal modification (Table 2)
6. Heart injury as determined by serum troponin levels.
7. Renal inflammation as determined by urine NGAL concentrations.
8. Allogenic red cell transfusion volume.
9. Non red cell transfusion volume.
10. Time to discharge from Glenfield Hospital ICU.
11. Time to Glenfield Hospital discharge.
12. Measures of haemoglobin metabolism e.g. serum hepcidin, serum haptoglobin, transferrin saturation, serum ferritin, plasma labile iron concentrations.
13. Inflammatory cytokines in serum, measured by IL-6, IL-8, TNF α , MCP-1 and MIP-1.
14. Other adverse events not specified above.

Feasibility outcomes

15. Recruitment, sampling rates, and Withdrawal rates
16. Protocol adherence including clinical and laboratory protocol adherence
17. Data completeness
18. Experience of parents/ family/ guardians in relation to the screening, consent and study procedures based on a questionnaire

Table 1. Pediatric KDIGO-staging system for acute kidney injury, as per reference [1], with modified Stage 3 as per the pRIFLE definition [2].

Stage	Serum creatinine (SCr) criteria	Urine output criteria
1	SCr \geq 26 $\mu\text{mol/L}$ increase or SCr \geq 1.5- to 2-fold from baseline	<0.5 ml/kg/hr for > 6 consecutive hrs
2	SCr \geq 2 to 3-fold from baseline	<0.5 ml/kg/hr for > 12 hr
3	SCr \geq 3-fold from baseline or SCr \geq 354 $\mu\text{mol/L}$ or Renal replacement therapy irrespective of stage or *Decrease in estimated Creatinine Clearance (eCrCl) to less than 35 mL/min/1.73 m ² using the Schwartz equation: eCrCl(mL/min/1.73 m ²) = (36.2 \times Height in cm) / Creatinine in $\mu\text{mol/L}$	<0.3 ml/kg/hr for > 24 hr or anuria for 12 hr

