The above criteria include both an absolute and a relative change in creatinine to accommodate variations related to age, gender, and body mass index and to reduce the need for a baseline creatinine but do require at least two creatinine values within 48 hours. Only one criterion (creatinine or urine output) has to be fulfilled to qualify for a stage. 200% to 300% increase = 2- to 3-fold increase. Given wide variation in indications and timing of initiation of renal replacement therapy (RRT), individuals who receive RRT are considered to have met the criteria for stage 3 irrespective of the stage they are in at the time of RRT. The modified stage 3 criteria for children* reflect the observation that infants with small body mass may be unable to generate high serum creatinine values.

Table 2. Neonatal acute kidney injury definition – modification from KDIGO pediatric AKI definition [3].

Stage	Serum creatinine (SCr) criteria Neonatal modification: 2015-2016	Urine output criteria Neonatal modification 2016
1	SCr \geq 26 $\mu\text{mol/L}$ increase or SCr \geq 1.5- to 2-fold from baseline	\leq 1 ml/kg/hr for 24 hr
2	SCr \geq 2 to 3-fold from baseline	\leq 0.5 ml/kg/hr for 24 hr
3	SCr \geq 3-fold from baseline or SCr \geq 221 $\mu\text{mol/L}$ or Renal replacement therapy irrespective of stage	\leq 0.3 ml/kg/hr for 24 hr

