2.3 Target conditions

1. Prolonged ECMO defined as patients remained on ECMO at day 7 (duration of ECMO >168 hours)
2. AKI as defined by the KDIGO stage 1, 2 or 3 using the paediatric AKI definition (Table 1).
3. AKI as defined by the KDIGO stage 1, 2 or 3 using the serum creatinine criteria for the neonatal AKI definition (Table 2).

3. Analysis Sets/Populations

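### Does SAP 4.5 need to say which AKI definition forms its groups with and without AKI?

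*SAP*

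**What the plan says.** SAP 4.5 reads "Exploratory analysis may be carried out to assess the relationship of cellular activation with the targeted subgroups". It then gives two groupings: time on ECMO split at 7 days, and "Patients with and without AKI". It names no table for the second.

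SAP 2.3 has three target conditions. The first is ECMO lasting beyond 168 hours. The second is "AKI as defined by the KDIGO stage 1, 2 or 3 using the paediatric AKI definition (Table 1"), which takes in the whole of Table 1. The third is restricted to AKI defined "using the serum creatinine criteria for the neonatal AKI definition (Table 2"). SAP 2.2 lists the two definitions as separate secondary outcomes, the neonatal one as "AKI as defined based on the neonatal modification (Table 2") without that restriction.

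Table 1 has two routes to AKI that condition 3 lacks. One is "Decrease in estimated Creatinine Clearance (eCrCl) to less than 35 mL/min/1.73" m², explained by the remark that "infants with small body mass may be unable to generate high serum creatinine values". The other is urine output, starting at "<0.5 ml/kg/hr for > 6 consecutive hrs" for Stage 1. The note under Table 1 lets either creatinine or urine output qualify by itself.

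The protocol (5.3.2, Table 1) has a single KDIGO-based definition with the same clearance criterion.

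**The concern.** One AKI bullet in SAP 4.5 faces two AKI target conditions that need not agree on the same infant. SAP 4.5 is also the only listed analysis that relates the activation markers to AKI, which is secondary hypothesis 3; the SAP 4.4 list has NGAL but no AKI item. SAP 1.3 cites marker differences by AKI status in a similar study as part of the reason for enrolling 24.

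If the definition is open, group membership could be settled after the data are seen, and SAP 4.6 makes no multiplicity adjustment. A reader planning the definitive study might then not know which kind of AKI a marker difference refers to. Two inputs are also unnamed: the creatinine value that serves as baseline, and the status of an infant whose clearance is already below 35 at that point.

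**Working it through.** The plan gives no figure to reproduce; SAP 1.3 states that there was no formal power calculation. The check codes the two conditions from the SAP's tables and asks where they differ. Lengths of 45, 50 and 55 cm are assumptions, because the documents give none.

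**1. Reading SAP 4.5.** SAP 4.3 calls the SAP 2.3 list the targeted conditions, and SAP 4.5 uses the same adjective for its subgroups. The 7-day bullet corresponds to condition 1 (7 × 24 = 168 hours). The AKI bullet corresponds to conditions 2 and 3. On this reading both are used.

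**2. Clearance route.** The SAP's formula is eCrCl = 36.2 × height / creatinine. It equals 35 at creatinine C = 36.2 × height / 35:
- 45 cm: 46.5 µmol/L
- 50 cm: 51.7 µmol/L
- 55 cm: 56.9 µmol/L

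Take 50 cm and creatinine going from 40 to 53. eCrCl goes from 1810/40 = 45.3 to 1810/53 = 34.2, so condition 2 is met. The rise is 13 (limit 26), the ratio 53/40 = 1.33 (limit 1.5) and the value is below 221, so condition 3 is not met.

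**3. Range of baselines.** Suppose the criterion requires eCrCl to cross 35. Clearance alone then changes the label when b < C and min(1.5b, b + 26) > C. At 50 cm that gives b from 51.7/1.5 = 34.5 up to 51.7. If being below 35 is enough, the upper limit C no longer applies: a steady 60 µmol/L at 50 cm gives 1810/60 = 30.2, which is AKI under condition 2 only. The range therefore depends on how the criterion is read.

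**4. Urine route.** At 50 cm, creatinine going from 40 to 45 (eCrCl 40.2) with urine output under 0.5 ml/kg/hr for more than 6 hours is AKI under condition 2 and not under condition 3.

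**5. Direction of disagreement.** A grid of baselines from 10 to 298, later values up to 398 and heights of 35 to 60 cm found no infant with AKI under condition 3 only, when the criterion is read as being below 35. The reason is that a creatinine of 221 at 50 cm gives eCrCl 1810/221 = 8.2. Condition 3 then sits inside condition 2. The number labelled differently is the condition 2 count minus the condition 3 count, and SAP 4.3 already reports both. If a crossing is required, there is one exception: a baseline of at least 196 with a later value of at least 221 and a rise under 26.

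**6. Reference creatinine.** Protocol 6.5 measures creatinine by study assay from 12 h, the time point that Protocol 5.3.1 and SAP 1.5 call baseline. The SAP Appendix also lists a routine pre-ECMO creatinine. With 40 pre-ECMO, 50 at 12 h and a peak of 62, condition 3 is met against the first (+22, 62/40 = 1.55) and not against the second (+12, 62/50 = 1.24). So the choice can matter for an individual infant. It is a derivation step for every AKI outcome, not a fault of SAP 4.5.

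**7. Neonatal urine column.** An output of 0.8 ml/kg/hr for 24 h with no creatinine rise meets the Table 2 urine criterion and neither target condition. SAP 2.3 limits its neonatal condition to creatinine, so this version is not a candidate grouping for SAP 4.5.

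**The case for a change.** The strongest case for a change is that the link to SAP 2.3 is only inferred, and with 24 infants a few reclassifications would show. As an illustration, apply the 64% AKI figure from Protocol 3.2: 0.64 × 24 ≈ 15 with AKI and 9 without under condition 2. If four of the 15 qualified only by clearance or urine output, condition 3 would give 11 and 13. Assume a true 1.2 SD marker difference between the condition 2 groups and two-sided alpha 0.05. Grouping by condition 3 would then lower approximate power from 0.81 to 0.53. A few sentences in the SAP would remove the doubt at almost no cost.

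Part of this stands: the definitions do differ, SAP 4.5 has no explicit cross-reference, and adding one would be harmless. The rest carries less weight. The four infants and the 1.2 SD are assumptions, and the illustration takes condition 2 as the true grouping, which the documents do not establish. Power is not the aim here; Protocol 7.3 and the synopsis describe a descriptive analysis that feeds a later design. The SAP introduction openly allows unplanned exploratory work, so naming a definition would not close off other groupings. The AKI definition used in the earlier study of 24 children is not given in these documents, so naming one here would not alter the basis for the sample size.

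**Conclusion.** The observation is accurate, but it is a missing detail and not an error. No stated rule gives a wrong result. Under the natural reading of SAP 4.5 the comparison, if run, is made under both AKI target conditions, and SAP 4.3 has both proportions reported, so a reader will see how far they differ. An analyst would label each comparison with its definition and state the reference creatinine used.

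The size cannot be fixed from the documents. Labels can differ through clearance below 35 (creatinine above about 46.5 to 56.9 µmol/L for assumed lengths of 45 to 55 cm) or through urine output alone, and the number of infants may be zero. Only an optional, exploratory comparison is affected, with no decision, threshold or primary result depending on it. This conclusion rests on reading SAP 4.5 as pointing to SAP 2.3 and on the results being presented as exploratory, as the SAP describes them. No change to the plan is needed.

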4.6 Multiple Comparisons

There will be no adjustments for multiple comparisons, as this is a feasibility study to gather data on the primary and secondary outcomes for future study, and to explore the relationship between these outcomes to address the objectives described above.

4.7 Handling of Missing Data

Lab measurements below the limit of quantification will be imputed as half the limit of quantification. Measurements above the limit of quantification will be imputed as the upper limit. No other missing values will be imputed.

5. Safety Analysis

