2. Withdrawal rate and completeness of follow-up and data collection in a paediatric population at high risk for death and major morbidity.
3. The proportions (categorical data) and variance (continuous data) for the primary and secondary outcomes of interest. These will be used to model the sample sizes and outcomes that may be used in a definitive study.
4. Perceptions of family members, whose children participate in the study as to the appropriateness of the screening and consent process. (Appendix 1)

5. Plan of Investigation

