1.1 Aims and Objectives

Hypothesis

The primary hypothesis is that damage to red blood cells by the exposure to the ECMO circuit will result in inflammatory responses that mitigate against successful weaning from ECMO for PPHN.

The secondary hypothesis are:

1. Damage to red cells will result in platelet, leukocyte and endothelial activation.
2. Markers of platelet, endothelial and leukocyte activation are indicators of lung inflammation and injury severity and hence lung recovery.
3. Markers of platelet, endothelial and leukocyte activation are indicators of kidney injury severity and hence acute kidney injury.
4. Granulocyte and platelets activation are secondary to rising redox potential and the levels of activation will correlate with longer intubation times and more severe organ injury.
5. Markers of platelet, endothelial and leukocyte activation have diagnostic and prognostic utility for the prediction of key clinical events including delayed time to recovery, acute kidney injury in paediatric patients undergoing ECMO for PPHN.

Objectives

The Mi-ECMO study was designed to be a feasibility study, and the results will be used to assist with the design of a prospective observational study that will test the above hypotheses. The objectives of the study are:

1. To determine the recruitment rates and patient flows for 24 patients recruited for the feasibility study.
2. To determine the withdrawal rate and the completeness of follow-up and data collection in a paediatric population at high risk for death and major morbidity.
3. To collect data on primary and secondary outcomes of interest, which may be used to model the sample sizes and outcomes in future study.
4. To collect data on perception of family members, whose children participate in the study, as to their understanding of the screening and consent process (Appendix 1).

Changes in hypothesis

Due to the lack of ethical approval, this study is not conducting analysis of bronchial aspirates, and measuring markers of oxidative stress and MV levels. The following secondary hypothesis which were stated in the study protocol have not been included in this SAP:

1. The level of oxidative stress will correlate with type shifts in pulmonary macrophages, tissue iron deposition and organ injury.
2. Ability to raise anti-oxidative response, measured by Heme Oxygenase-1 (HMOX 1) expression, will correlate with shorter intubation times and less severe kidney and lung injury.

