4.3 Descriptive Analysis

Descriptive analysis will be presented for demographic and baseline characteristics, as well as the primary and secondary outcomes, and targeted conditions described in Section 2. For categorical variables, numbers and percentages will be presented. For continuous variables, mean and standard deviation or median with lower and upper quartiles, as appropriate, will be presented.

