4.4 Statistical Methods

Mixed effects model with patient as random effect will be used to analyse outcomes measured at multiple time points. Logarithm transformation will be considered for skewed variables. Linear graphs showing the variation of the mean measurements over time will be displayed.

Exploratory analysis are to be carried out using mixed effects models to examine serial makers of cellular activation and their relationship with:

- Duration on ECMO

- Transfusion volume
- Free cell haemoglobins
- NGAL concentrations
- Serum troponin levels
- Inflammatory cytokines

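### Setting above-range assay values to the upper limit always understates the SD, LOQ/2 can move it either way, and these SDs are meant to size the next study

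*SAP*

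**What the plan says.** SAP 4.7 has three rules. Below range: "Lab measurements below the limit of quantification will be imputed as half the limit of quantification". Above range: "Measurements above the limit of quantification will be imputed as the upper limit". Everything else: "No other missing values will be imputed". It plans no censored-data method, no sensitivity analysis and no count of replaced values. The completeness summary in SAP 4.2 does not ask for such a count either.

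The results then pass into two places. SAP 4.3 describes continuous variables by "mean and standard deviation or median with lower and upper quartiles, as appropriate, will be presented". SAP 4.4 fits mixed models to the serial measurements, and "Logarithm transformation will be considered for skewed variables". Protocol 7.3 reports non-normal data as geometric means, which also implies a log scale.

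The third protocol objective is to obtain "The proportions (categorical data) and variance (continuous data) for the primary and secondary outcomes of interest", for modelling the sample size of a definitive study. SAP 1.1 keeps that use: "To collect data on primary and secondary outcomes of interest, which may be used to model the sample sizes and outcomes in future study". Protocol 7.3 repeats it.

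**The concern.** A value outside the limits is known only to lie beyond a point. SAP 4.7 turns it into an exact number, and the models then treat it as observed. That alters the spread, and spread is one of the things the study hands to its successor. An SD that is too small gives an undersized next study; one that is too large wastes scarce neonates. If the share of replaced values is not reported, a later planner cannot tell how far, or in which direction, a given SD has moved.

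The outcomes most exposed are those measured by immunoassay. These are ICAM and E-selectin among the primary markers, and the cytokines, troponin, urine NGAL and hepcidin among the secondary ones (Protocol 6.5, SAP 2.1 and 2.2).

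**Working it through.** **Inputs.** The two substitution rules come from SAP 4.7. The documents give no assay limit, marker SD or expected out-of-range share, so there is no plan figure to reproduce. Log-normality, log-SDs of 0.5 to 2 and the shares below are assumptions.

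**1. Upper limit: direction.** A sample variance is proportional to the sum of squared differences between pairs of values. For any two values, |min(x, U) − min(y, U)| ≤ |x − y|. Capping therefore cannot raise the total SD, on the raw or the log scale and for any distribution.

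**2. Upper limit: size.** Take a standard normal Z with share q above c = Φ⁻¹(1 − q), and Y = min(Z, c).
- E(Y) = −φ(c) + cq
- E(Y²) = (1 − q) − cφ(c) + c²q
- q = 10%: c = 1.2816, φ = 0.1755, E(Y) = −0.0473, E(Y²) = 0.8393, variance 0.837, SD ratio 0.915
- q = 20%: c = 0.8416, φ = 0.2800, E(Y) = −0.1116, E(Y²) = 0.7060, variance 0.694, SD ratio 0.833

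The ratio does not depend on the true SD. At 5% and 30% it is 0.957 and 0.751. Sample size scales with variance, so it is understated by 1 − 0.837 = 16% at 10% above range and 1 − 0.694 = 31% at 20%.

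**3. LOQ/2: direction and size.** On the log scale the substituted value is ln(LOQ) − ln 2. In units of the true log-SD σ, with a = Φ⁻¹(p), it is d = a − 0.693/σ.
- Mean = pd + φ(a)
- Second moment = pd² + (1 − p) + aφ(a)

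With p = 20% (a = −0.8416):

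| σ | d | Mean | Second moment | Variance | SD ratio |
|---|---|---|---|---|---|
| 0.5 | −2.228 | −0.166 | 1.557 | 1.530 | 1.24 |
| 1 | −1.535 | −0.027 | 1.036 | 1.035 | 1.02 |
| 2 | −1.188 | 0.042 | 0.847 | 0.845 | 0.92 |

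The rule shrinks the SD only when σ exceeds a crossover: 1.54 with 5% below, 1.33 with 10%, 1.09 with 20%, 0.93 with 30%, 0.80 with 40% and 0.69 with 50%. For σ of 0.6 or less it inflated the SD at every share up to 50%.

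**4. Both ends together.** With 20% outside each limit the ratio is 1.09 at σ = 0.5 and 0.85 at σ = 1.

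**5. Consequence for a later study.** Assume a ratio of geometric means of 1.5, two-sided 5% and 80% power. Then n per group = 2(1.960 + 0.842)²σ²/(ln 1.5)².
- σ = 1: 96 per group are needed. The capped SD at 20% above gives 67, with a real power of about 65%.
- σ = 0.5: 24 per group are needed. The LOQ/2 SD at 20% below gives 37, with a real power of about 94%.

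**6. Contrasts.** For two equal groups 0.8 SD apart, capping keeps 91% of the mean difference at 10% above range, 81% at 20% and 61% at 40%. LOQ/2 with 40% below keeps 87% at σ = 1 and 74% at σ = 2.

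**7. Does the alternative work at this size?** In simulations of 24 patients at 5 time points (intraclass correlation 0.5 assumed), a censored mixed model had a lower root mean squared error for the SD ratio than substitution in every upper-limit scenario. At 20% above and σ = 1 the errors were about 0.10 and 0.19. It also did better in most LOQ/2 scenarios, and lost slightly only at 20% below with σ of 1 to 1.5.

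**The case against.** There are four serious counter-arguments.

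- **Occurrence is not shown.** No assay limit or expected share is given, and many primary markers are flow-cytometry measures for which nothing indicates that limits matter. This stands. It is why every size here is conditional and why the remedy is triggered by the observed share.
- **Quartiles may suffice.** With fewer than 25% of values beyond a limit, the median and quartiles are untouched by either rule, and SAP 4.3 permits them. This is correct as far as it goes. But SAP 4.3 leaves the choice open, nothing says a later planner would derive the spread from quartiles, and the SAP 4.4 models use the substituted values.
- **Sampling error is larger.** Even with complete data an SD from 24 infants has a relative error of about 1/√(2 × 23) = 15%, and a single-sample Tobit fit at n = 24 can be less accurate than substitution (0.167 against 0.124 at σ = 1 with 20% below). This is fair for one time point. It largely disappears once all five time points are used, as in step 7. Sampling error can also be put into a confidence interval, whereas bias from an unreported share cannot.
- **Importance is limited.** Variance is part of one of four objectives, and the SAP 4.5 contrasts are exploratory and optional. This stands too.

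A reader might also infer that the two rules together generally bias the variances low and so leave the next study undersized. The documents do not support that. The direction of the LOQ/2 error depends on each marker's log-SD and share below the limit, and neither is given. At modest log-SDs the next study would be too large.

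**Conclusion.** The point holds in a limited form. Capping at the upper limit always understates the total SD once a value is capped, and this needs no distributional assumption. Under log-normality the SD is about 0.91 of the truth at 10% above range and 0.83 at 20%. LOQ/2 can understate or overstate the log-scale SD, with ratios from 1.24 to 0.92 at 20% below for log-SDs of 0.5 to 2. Because the plan records no out-of-range shares, the error in any reported SD could not be judged afterwards.

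It would be too strong to say that the study exists to supply these variances, since recruitment, withdrawal and completeness, and family perceptions are objectives as well. If few values fall outside limits, the effect is small. This is a cheap improvement and does not invalidate the plan.

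**What to change.** Amend SAP 4.7 as follows.

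1. For each marker and time point, tabulate the number and percentage of values below and above the assay limits.
2. For any immunoassay marker with more than about 10% of values outside limits, estimate the log-scale mean, variance components and contrasts with a censored-normal (Tobit) mixed model using all time points. Report the substitution result alongside.
3. Keep the present substitution for markers at or below that share.

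The 10% trigger is a judgement and should be fixed before the data are analysed. The table costs almost nothing. The model costs a little more analysis in standard software, relies on log-normality in the tails, and gives slightly wider sampling error where LOQ/2 happens to be near neutral (log-SD about 1 to 1.5 with about 20% or less below the limit). Showing both results lets a later planner see how much the choice matters.
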